In each CNC about 20 children are expected to suffer from moderate malnutrition.

The study hypothesis is that there will be no difference in improvement between intensive nutrition education group and less intensive education group in proportions improving from moderate malnutrition receiving nutrition education. The study will disprove the hypothesis if a 15% difference is detected with statistical significance.

$$\text{Using formula } n = \frac{p_1(1-p_1) + p_2(1-p_2)}{(p_1 - p_2)^2} (z_{\alpha} + z_{\beta})^2$$

(Reference: G W Snedecor and WG Cockran. Statistical Methods in Medical sciences. Oxford Publications 6th edition 1968, pp 111-114). Where p_1 is proportion of reduction of moderate malnutrition in intensive nutrition intervention group and p_2 is reduction in proportion of malnutrition in less intensive education group and $(z_{\alpha} + z_{\beta})$ is the function of level of significance and power of the statistical test.

$p_1=0.5$ and $p_2=0.35$

where z_{α} = level of significance at 5%, =1.96

and z_{β} = power of the study 90%, =1.28

where $(p_1 - p_2)$ = difference of proportion moving to mild malnutrition between control and intervention group.

$$n = \frac{0.5 \times 0.5 + 0.35 \times 0.65}{(0.15)^2} \times 10.5 = 222.$$

Taking a cluster effect of the design as the children will be selected from CNC s this is increased to $222 \times 1.5 = 333$. with a drop out possibility of 10%, it will be about 366 children in each group.

Total sample size will be $366 \times 2 = 732$ or 750 subjects.

Sample size for preventive study group:

Assumption is that mildly malnourished children will usually slip into moderate malnutrition without any nutrition education but with less intensive nutrition education, they will not slip into malnutrition. The study will be interested to detect a difference of 20% with a 5% probability and

90% power.

[figure not shown]
To detect this 20% difference the number of mildly malnourished children in two study groups will be $(121 \times 2) = 242$. The cluster effect of randomization by CNCs will be controlled by multiplying the number by a factor of 1.5 i.e. $242 \times 1.5 = 363$ for mildly malnourished groups and possible drop out (10%) can be covered with a total number of $(190 \times 2) = 380$ subjects.

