As almost 80% of the 6-9 month old infants will be included in mild and moderate groups, rest 20% who are well nourished will be studied with less intensive education for preventive approach. There will be $(50 \times 2) = 100$ infants in 6-9 month old group to receive either less intensive education on complementary feeding or no education. These well nourished infants will be analyzed separately to see if less intensive education on complementary feeding prevents them from falling to mild or moderate malnutrition.

Selection and randomization procedure: (Tables 1,2,3)

For management approach the number of subjects will be 375 in each group and a total of 750 children will be selected from 40 CNCs from 4 divisions. One thana will be randomly selected from each Division, and two unions will be randomly selected from each thana, and 5 CNS will be randomly selected from each union. From a total of $(5 \times 2 \times 4) = 40$ CNCs, 20 will be allocated for intensive education and 20 will be randomly allocated for less intensive education.

To avoid contamination for the control groups with no nutrition education in the preventive approach, 8 additional CNCs will be randomly selected one from each union of the four divisions. Finally in each union 5 CNCs will be under either intensity of education and one CNC will be with no education. A diagram is given below:

LINE : Less intensive nutrition education, INE : Intensive nutrition education

Table 1

Sample selection

Subjects	Intensive education	Less intensive education	No education	Total
Moderately malnourished	375	375	---	750
Mildly malnourished	---	190	190	380
6-9 months old infants	---	50	50	100
CNCs	20	20	8	48

Table 2

RANDOMIZATION PROCEDURE

[figure not shown]
[figure not shown]

Table 3

Selection procedure

Randomization procedure:

(a) Total number recruited moderately malnourished children are 750. They will be selected equally from 40 CNC's in two study groups. Individual child will not be randomized but the children in each CNC as a group will be allocated randomly to either of the two study groups according to a random number table. Identified 5 CNC's in each union will be randomly allocated by their identification numbers to one of the two study groups.

(b) In the preventive group, mildly malnourished children will be randomized by CNCs for less intensive nutrition education or no nutrition education.

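### The preventive sample of 380 covers a loss of about 4.5%, not the stated 10%; with 10% loss, power is about 88% rather than 90% (minor)

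*Protocol*

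**What the plan says.** The calculation is in the protocol under the heading Sample size for preventive study group. The target is stated as "The study will be interested to detect a difference of 20% with a 5% probability and" 90% power. The protocol gives 121 children per group, 242 in all. It then allows for allocation by community nutrition centre (CNC) by "multiplying the number by a factor of 1.5 i.e. $242 \times 1.5 = 363$ for mildly malnourished groups". Last, it states that "possible drop out (10%) can be covered with a total number of" 190 × 2 = 380. Table 1 repeats 190 + 190 = 380.

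The management calculation just above it handles the same allowance differently. It goes from 333 per group after the factor of 1.5 to the next figure: "with a drop out possibility of 10%, it will be about 366 children in each group".

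**The concern.** The step from 363 to 380 is an increase of less than 5%, yet it is said to absorb a 10% loss. The same section adds the full 10% for the management groups. So the protocol gives two comparisons the same stated dropout allowance, and one of them gets less than half of it.

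At stake is whether the stated 90% power holds at the loss the protocol itself expects. This is the only prevention comparison with a sample size calculation (the 50 + 50 well-nourished infants have none), and prevention is part of the first primary objective. Children are followed for 6 months of education and 6 months of observation. If the comparison showed no difference, readers would judge that result against the stated power.

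**Working it through.** **Inputs.** From Sample size for preventive study group: 121 per group, cluster factor 1.5, 10% dropout, 190 per group, 90% power. From the management calculation: z = 1.96 ("level of significance at 5%, =1.96"), z = 1.28, their squared sum rounded to 10.5, and the formula n = [p1(1−p1) + p2(1−p2)] / (p1−p2)² × 10.5. The two proportions behind 121 are not in the text at hand. I assume 0.50 and 0.30 to check that 121 is plausible; the main results below do not depend on them.

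**Reproducing the protocol's figures.**
- n = (0.25 + 0.21) / 0.04 × 10.5 = 120.75, so 121 per group. The pair 0.70 and 0.50 gives the same value.
- 121 × 2 = 242.
- 242 × 1.5 = 363.

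Everything up to 363 reproduces.

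**The dropout step.**
- By the protocol's method for the management groups (333 × 1.1 = 366.3): 363 × 1.1 = 399.3, so 400 in two equal groups of 200.
- By the usual method: 363 / (1 − 0.10) = 403.3, so 404, or 202 per group.
- Protocol: 380. The shortfall is 20 to 24 children.
- Loss that 380 can absorb: (380 − 363) / 380 = 17 / 380 = 4.5%.

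For comparison, the management groups are rounded up to 375 each, which absorbs (375 − 333) / 375 = 11.2%.

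**Power with 10% loss.**
- Children remaining: 380 × 0.9 = 342, or 171 per group. This is 21 fewer than 363.
- Effective size: 171 / 1.5 = 114 per group, against 121 required.
- Power, scaled from the protocol's own target: Φ[(1.96 + 1.2816) × √(114/121) − 1.96] = Φ(1.186) = 88.2%. The hidden proportions cancel out of this formula.
- Direct check with 0.50 and 0.30: Φ[0.2 / √(0.46/114) − 1.96] = 88.3%.
- With a pooled-variance test and the same proportions, power is 87.4%, against 89.3% at 121 per group. The drop is again about 2 points.

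| Enrolled per group | Effective size after 10% loss | Power (scaled) |
|---|---|---|
| 190 (protocol) | 114 | 88.2% |
| 200 | 120 | 89.8% |
| 202 | 121.2 | 90.0% |

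With no loss at all, 190 per group is worth 126.7, and power under 0.50 and 0.30 is 91.3%.

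**The case against.** The strongest reply is that this hardly matters. The shortfall is 20 to 24 children and the power falls by about 1.8 points. No analysis, allocation or conclusion changes. That stands, and it is why the point is minor. It does not make the dropout statement correct.

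A reader might go further and infer that power is well below 88% because the flat factor of 1.5 ignores the layout. The protocol says "Finally in each union 5 CNCs will be under either intensity of education and one CNC will be with no education", so the 190 controls sit in 8 CNCs (about 24 each) and the 190 children given less intensive education sit in 20 CNCs (about 9.5 each). The documents do not support that inference:
- The protocol gives no intracluster correlation (ICC). One can be back-calculated from the management groups, at 375 / 20 = 18.75 children per CNC: 0.5 / 17.75 = 0.028. That carries it over to different children and a different outcome.
- At 0.028 and 171 children per group, the design effects are 1 + (171/8 − 1) × 0.028 = 1.57 for controls and 1 + (171/20 − 1) × 0.028 = 1.21 for education. Their average, 1.39, is below 1.5. By the protocol's normal approximation, with 0.50 in controls and 0.30 with education, power is about 90%.
- A figure near 86% appears only if a t correction with about 16 degrees of freedom is added, which the protocol's formula does not contain. With that correction the result runs from about 93% at an ICC of 0.01 to about 78% at 0.05. One value from that range cannot be put forward as the power of this design.

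**Conclusion.** The point holds as an inconsistency between the sample size and its dropout allowance. The figure 380 covers about 4.5% loss; the stated 10% would need 400 or 404, depending on the method. This follows from printed figures alone and does not depend on the missing formula.

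The consequence is small: about 88% power with 10% loss, against 90% stated. This takes as given the protocol's factor of 1.5, its normal approximation, a two-sided 5% level (inferred from z = 1.96) and equal loss in both groups. It would be wrong to read it as a serious loss of power, or as evidence that the split between 20 and 8 CNCs makes the shortfall worse. Severity: minor.

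**What to change.** Keep 190 per group and correct the sentence, for example: the total of 380 allows for about 4.5% loss after the cluster factor of 1.5; with 10% loss, power to detect a 20-point difference is about 88%.

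The cost is a slightly less favourable stated figure. No extra children, CNCs or budget are needed, and Table 1 stays as it is. Enrolling 400 to 404 would also settle it, but would recover less than 2 points of power.

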Collection of morbidity data:

Morbidity information will be collected at two weekly home visits during study period using pre-tested questionnaire.

Operational definition

Fever: If the temperature is more than normal, that is above 38.5⁰ C is called fever.

In the field level:

1. When mother tell about her child suffered from fever that lasted for 1 day, a physician will examine the child and child will be treated at home for mild fever.
2. When mother will tell that her child has fever lasting for two to three days, it will be regarded it as moderate fever.
3. Mother will tell that fever lasts for more than three days, he will be examined and regarded as sever fever.

Diarrhoea: An episode of diarrhea is defined as the passage of three or more loose or watery stools within 24 hours. Records will be collected on consistency and the number of stools per day.

1. A child passing loose, liquid or watery stool more than three times per day will be called acute diarrhoea.
2. Presence of blood with stool will be define as invasive diarrhea.
3. When a single episode of diarrhea lasts for more than two weeks, it will be called persistent diarrhoea.

Ear Infection: A child will have pain in ear, fever, with watery or purulent secretion from one or both ear will be diagnosed as ear infection.

Lower respiratory tract infection: When a child suffering from cough and fast breathing more than 50 per minute, fever, or chest indrawing will be defined to have lower respiratory tract infection (LTRI).

Upper respiratory tract infection: A child suffering from cough and cold without sings of LRTI will be diagnosed as upper respiratory tract infection (URTI).

Skin infection: A child suffering from skin disease with impetigo or skin infection or scabies will be define have skin infection.

Sore on Tongue: Ulceration or fissure on tongue or palate will be identified as sore tongue.

Angular stomatitis: Any child having signs of ulceration or excoriation in angle of mouth will be diagnosed to have angular stomatitis.

Xerpthalmia : Conjuntival haziness & corneal haziness will be diagnosed as Xerophthalmia.

The subjects will be referred to THC by interviewers during two weekly home visits if following conditions develop:

Referral will be done accordingly to IMCI criteria in the following ways:

1. Pneumonia: After 2 days of first time of antibiotic therapy:

Check the child for general danger signs.

Assess the child for cough or difficult breathing.

Ask:

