- Is the child breathing slower?
- Is there less fever?
- Is the child eating better?

Treatment:

- If chest indrawing or a general danger sign, give a dose of second-line antibiotic or intramuscular chloramphenicol. Then refer URGENTLY to THC.

2. Diarrhoea:

After 5 days:

Ask:

- Has the diarrhoea stopped?
- How many loose stools is the child having per day?

Treatment:

- If the diarrhoea has not stopped (child is still having 3 or more loose stools per day), do a full reassessment of the child. Give any treatment needed. Then refer to THC.

3. Dysentery:

After 2 days:

Ask:

- Are there fewer stools?
- Is there less blood in the stool?
- Is there less fever? Is there less abdominal pain?
- Is the child eating better?

Exceptions- If the child:

- is less than 12 months old, or
- was dehydrated on the first visit, or
- had measles within the last 3 months. Then refer to THC.

4. Ear-Infection:

After 5 days:

Ask:

- Is there ear pain?
- Is there ear discharge? If yes, for how long?

Look and feel:

- Look for pus drawing from the ear.
- Feel for tender swelling behind the ear.

Treatment:

- If there is tender swelling behind the ear or high fever (38.5°C or above), refer Urgently to THC.

5. Fever:

Ask:

- For how long?
- If more than 7 days, has fever been present every day?
- Has the child had measles within the last 3 months?

Look and feel:

- Look or feel for stiff neck.
- Look for runny nose

Look for signs of measles

- Generalized rash and
- One of these: cough, runny nose, or red eyes.

Treatment:

- Very severe febrile (high fever 38.5°C for above), then refer urgently to hospital.
- If fever is present every day for more than 7 days, refer for assessment.

Qualitative data collection methods

The baseline data will be collected through:

1. Survey
2. Focus group discussion
3. Participant observation:

Each method of data collection is elaborately mentioned bellow.

1. **Survey:** Information of socio economic condition of the respondents will be collected through direct questionnaire. These answers will cover the issues of family income, food status, education, occupation of the parents and also the size and type of the family.

2. **Participant Observation:** Participant observation will be conducted to explore basic feeding

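### Referral rules use 2- and 5-day checks but are applied at two-weekly home visits, and the dysentery rule states no day-2 action for a non-improving child outside its exceptions

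*Protocol*

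**What the plan says.** Under *Collection of morbidity data* the protocol sets the contact schedule: "Morbidity information will be collected at two weekly home visits during study period". After the operational definitions it assigns referral to the same contact: "The subjects will be referred to THC by interviewers during two weekly home visits if following conditions develop". It says that referral follows IMCI criteria and then prints five rules.

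- Pneumonia is checked "After 2 days of first time of antibiotic therapy". The action is: "If chest indrawing or a general danger sign, give a dose of second-line antibiotic or intramuscular chloramphenicol", followed by urgent referral.
- Diarrhoea is checked after 5 days: "If the diarrhoea has not stopped (child is still having 3 or more loose stools per day), do a full reassessment of the child", then treatment and referral.
- Dysentery is checked after 2 days, with questions on stools, blood, fever, abdominal pain and eating. The only action stands at the end of a list of exceptions: age under 12 months, a child who "was dehydrated on the first visit", or one who "had measles within the last 3 months. Then refer to THC".
- Ear infection is checked after 5 days, with urgent referral for swelling behind the ear or high fever.
- Fever has no check day. It is referred urgently if high, or for assessment if present daily for more than 7 days.

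The *Operational definition* of diarrhoea adds: "When a single episode of diarrhea lasts for more than two weeks, it will be called persistent diarrhoea". It also classes blood in the stool as a form of diarrhoea.

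**The concern.** The check days and the contact schedule do not fit together, and the text does not say how they should. The days may be due dates for a re-check; the dysentery wording about a first visit points that way. They may instead be durations asked about at whatever visit comes next, as in the fever rule. Under either reading, a child who is ill at a visit but not yet at the threshold has no scheduled home contact for a fortnight.

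The dysentery rule raises a separate problem. It collects answers about improvement and then does not use them: the stated referral depends on age, dehydration and measles history, not on whether the child is better.

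At stake is the care of sick children. *Table 1* plans 750 + 380 + 100 = 1,230 children, of whom 750 + 380 = 1,130 are mildly or moderately malnourished. *Ethical Assurance* names referral to the local health system as the provision for severe illness.

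**Working it through.** The protocol gives no figure of its own here, so the check sets the rules beside the visit interval.

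**Interval.** Two-weekly means every 14 days. The section on focus group discussions uses the term for an interval, and Annexure 4 describes the same education in the earlier study both as two-weekly and as given twice in a month.

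**Rules as printed.**

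| Rule | Check time | Treatment line? |
|---|---|---|
| Pneumonia | 2 days from first antibiotic | Yes |
| Diarrhoea | 5 days | Yes |
| Dysentery | 2 days | No; exceptions list only |
| Ear infection | 5 days | Yes |
| Fever | None; duration over 7 days | Yes |

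Four of the five rules carry a 2- or 5-day check. No home visit is scheduled on those days.

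**Due-date reading.** Assume that illness is first seen, or treatment starts, at a home visit (day 0). The next home visit is day 14.

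- Day-2 check: 14 − 2 = 12 days after it is due.
- Day-5 check: 14 − 5 = 9 days after it is due.

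For pneumonia the clock starts with the antibiotic, which may be given elsewhere between visits. If it starts k days after a visit (k from 0 to 12), the next home visit falls 14 − (k + 2) = 12 − k days after the check is due. That runs from 12 days down to none, so 12 days applies only when therapy starts on a visit day.

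**Duration reading, for diarrhoea.** Let d be the days of diarrhoea at a visit, with d = 1 to 4, below the 5-day rule.

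- If it does not stop, duration at the next visit is d + 14 = 15 to 18 days.
- Time past the threshold is d + 14 − 5 = 10 to 13 days.
- All four values exceed 14 days, so the child already meets the protocol's own definition of persistent diarrhoea.

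**Dysentery.** Take a child over 12 months, not dehydrated at the first visit and without recent measles, who is no better at day 2. The dysentery block states no action. Because bloody stool counts as diarrhoea, the diarrhoea rule applies from day 5 if the child still has three or more loose stools a day, which is 5 − 2 = 3 days later on paper. High fever would trigger the fever rule at any time. A child with continuing blood but fewer than three loose stools a day and no high fever meets neither of these.

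**The case against.** The best defence is that this is ambiguity, not contradiction. If all the days are durations, the rules can be applied at two-weekly visits; referral is said to follow IMCI, and *Quality control measures* promises detailed manuals, either of which may supply the missing dysentery line. That is possible, but the rules printed are the ones given to staff, and the duration reading still leaves the 15-to-18-day result.

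The second defence is that other contacts exist. Education sessions reach the INE and LINE groups during the six-month intervention, weighing is monthly over that period, a physician examines a child with one day of fever, and a medical officer teaches timely referral. Mothers can also go to the THC or FWC themselves. These may shorten the wait, but none is assigned a re-check. The no-education groups (190 + 50 = 240 children) have no study sessions.

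A reader might infer four stronger things that the documents do not support.

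- *That a non-improving child with dysentery gets no action at all.* The day-5 diarrhoea rule and the fever rule are backstops; the gap is at day 2.
- *That every pneumonia check is 12 days late.* The protocol does not say that interviewers start the antibiotic.
- *That time without education sessions measures the problem.* No re-check is assigned to those sessions, so counting months without them does not measure it.
- *That the trial comparison is biased.* The rules are worded alike for all groups.

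**Conclusion.** The point holds as a minor-to-moderate safety correction. Four of five referral rules use checks at 2 or 5 days that the stated contact schedule cannot meet. The lag is up to 12 or 9 days when illness is first seen or treated at a home visit. On the duration reading, unresolved diarrhoea of 1 to 4 days is next seen at 15 to 18 days. These figures count home visits only and assume a 14-day interval kept exactly. The dysentery rule lacks a day-2 action for a non-improving child outside its three exceptions. The documents do not allow a count of affected children, and no effect on the nutritional-status comparison is claimed.

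**What to change.** 1. Add to the dysentery rule: *not improving after 2 days, refer to THC*. Keep the exceptions.
2. The *Project Summary* and Annexure 2 already promise referral advice to all groups. Within that advice, tell every mother the specific thresholds and danger signs at which to go to the THC or FWC without waiting for the next visit. Include the no-education group and the observation phase.
3. State that at each two-weekly visit the days for diarrhoea, dysentery and ear infection are asked as illness duration, and the pneumonia days as time since the first antibiotic. Urgent signs are acted on whenever found.

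The third change settles the reading but does not shorten the 14-day interval; the second is what covers it. The medical investigators should confirm the wording; the day thresholds are the protocol's own.

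The cost is about half a page of protocol and manual text, with no extra visits or staff. This stays within the reply to the first reviewer (item 6), which rules out additional morbidity-control work. There are three limits. Timing will rest on mothers' recall over 14 days. Telling all mothers when to seek care may slightly dilute the care-seeking difference between LINE and no education. Annexure 4 also reports that mothers in the earlier study had trouble getting attention at the THC, so advice to attend does not guarantee care.
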